#### 6.6.1 Quality control

Barcoded amplicons of the variable V3-V4 region of the 16S rRNA gene will be sequenced on an Illumina MiSeq platform. Paired end fastq files will be demultiplexed and checked for remaining adaptors using FastQC. Further quality control on the raw reads and subsequent generation of Exact Sequence Variants (ESVs) can be done using the DADA2 package in  $R^{.19}$  In short, for each sequence run separately, reads are trimmed and filtered, sequence error rates are estimated, read abundance is calculated after dereplication and read pairs are merged. Next, sequence sets for the different runs are merged, and chimeric sequences and singletons removed. Optionally, spurious ESVs (e.g., relative abundance in no sample  $\geq 0.01\%$ ) can be removed from the final dataset. Taxonomic identification of the ESVs (reliable down to the genus-level) can be performed using the SILVA taxonomic database (version 138) with the RDP naïve Bayesian classifier method.

#### 6.6.2 Exploratory analysis

In addition to exploratory analysis embedded in QC, further exploratory analysis may be performed in R, using packages such as tidyverse, vegan and ampvis2. Principal component analysis (PCA) and other ordination analyses can be used to study the correlation of ESV abundance and different interventions. ESVs that explain most of the variation in the PCA can be identified using species. Multivariate statistics, such multivariate analysis of variance (PERMANOVA), on different distance measures can be used to validate the significance of correlations between interventions and the microbial community composition of the samples.

#### 6.6.3 Secondary outcome reporting

To report on the distinction of lean and obese/overweight individuals and smokers and nonsmokers, principal component plots will be generated and species plots will be provided.

To evaluate species diversity before and after intervention, richness indices such as the Shannon Diversity or inverse Simpson index will be reported before and after intervention. The relative gain or loss of beneficial and harmful individuals will be reported using ANOVA or Wilcoxon tests and visualised with barplots, and association of relative change could be associated with changes in epigenetic markers, BMI, or e.g. markers of gut leakiness (LBP).

A shift in dominant types and the association with stronger weight loss or epigenetic markers will be evaluated using heatmaps (e.g. the top 30 ASVs/genera/families). Subgroups of individuals where this shift does not occur will also be evaluated.

Functional pathway prediction will be done in R using the Tax4Fun2 package, evaluating pathways such as carbohydrate degradation, lipid metabolism, inflammatory properties, and hormone metabolism. A comparison may be conducted between individuals with and without ketogenic supplement in the diet intervention group.

#### 6.7 Blood data

From blood samples the following data will be generated:

- Lipid levels
- HbA1c
- c-reactive protein
- General immunological profile (cell subsets)

- T cell stimulation assay
- Cytokine and markers of inflammation

## 6.7.1 Quality control and exploratory analysis

Data will be generated using standardised protocols. Missingness of data will be visualised.

#### 6.7.2 Secondary endpoint reporting

Paired baseline-controlled analyses are used to compare month 0 and month 6 in each substudy. Linear mixed-effects models (potentially random slopes/intercepts) will be utilised to leverage longitudinal data and include further covariates. Change from baseline may be reported in a descriptive manner.

# 6.8 Metabolomic data

NMR profiling will be conducted which provides information on over 100 metabolites, including amino acids and organic acids.

## 6.8.1 Quality control and exploratory analysis

Data will be generated using standardised protocols. Missingness of data will be visualised.

#### 6.8.2 Secondary endpoint reporting

Data will be analysed in a longitudinal manner and changes associated with clinical parameters including markers of ketosis, where available, and fasting pattern (dinner or breakfast cancellation).

## 6.9 Skin data

Evaluation of ageing markers and barrier function may be conducted in a subgroup of participants for which skin data is available.

## 6.9.1 Quality control and exploratory analysis

Data will be generated using standardised protocols. Missingness of data will be visualised.

## 6.9.2 Secondary endpoint reporting

Paired baseline-controlled analyses are used to compare month 0 and month 6 separate for each sub-study.

# 6.10 Psychological data

## 6.10.1 Quality control and exploratory analyses

Data will be collected using standardised protocols. Missingness of data will be visualised.

## 6.10.2 Secondary endpoint reporting

Paired baseline-controlled analyses are used to compare month 0 and month 6 separate for each sub-study.

# 6.11 Subsidiary analysis: continuous compliance

Continuous compliance to intervention following the initial 6 months will be evaluate at month 6 and month 12 and reported in a summary table.

# 6.12 Subsidiary analysis: single cell sequencing

Single cell sequencing will be conducted to assess cell identity and population heterogeneity before and after two months of intermittent fasting, as well as chromatin accessibility and markers of senescence in cellular subgroups.

## 6.12.1 Quality control

Single cell analysis will follow current guidelines. A pilot experiment will be carried out to optimise sequencing depth. Sequencing data will be processed using the 10X Genomic cellranger or other available and validated tools at the time of analysis.

# 6.12.2 Exploratory analysis

Exploratory analysis may be conducted using Seurat for R, visualising cell heterogeneity and expression of genes across subgroups. Clustering of samples before and after intervention will be visualised.

## 6.12.3 Subsidiary endpoint reporting

The proportion of senescence-expressing immune cells and cells with lower-than-average PCGT chromatin accessibility will be reported. Visualisation of single cell populations before and after intervention (averaged over participants or per individual) will be carried out via two-dimensional projections such as UMAP. Changes may be taken into context with compliance of the individual.

# 6.13 Subsidiary analysis: epigenetic signatures of reprogramming

We will investigate whether DNAme regions or individual CpGs that change after Yamanaka factor reprogramming (OSKM) in blood cells (PBMCs) at month 0 also change during the intervention, in both smoking cessation and intermittent fasting.

## 6.13.1 Quality control

Cell death will be monitored in samples "before" and "after" reprogramming, and quality control will be in line with other epigenetic data.

## 6.13.2 Subsidiary endpoint reporting

We will investigate epigenetic changes before and after reprogramming in samples collected at baseline. The same regions identified here will be investigated in the same individuals at month 6, e.g. paired t-test mean or median methylation in significant CpGs before and after reprogramming and before and after intervention). For regions that change across participants, these can be investigated after intervention even in those individuals for whom no reprogramming analysis was conducted

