#### 2.2.3 Subsidiary outcomes or objectives

Subsidiary endpoints include analysis of longer-term changes at month 12 and 18 for participants who provided longer-term samples.

In a subgroup of participants (n=10), we will apply single cell multiomic analysis for RNA and ATAC-seq to investigate cellular heterogeneity at an early time point (two months

of intervention).

A subgroup of participants will be selected to investigate of which epigenetic sites are (individually) altered with cellular Yamanaka factor-induced reprogramming in samples collected at baseline (M0). In these participants we will investigated if the same or similar sites are significantly altered by the intervention at M6 (within-individual); if consistent regions are found across individuals, these sites may also applied to those individuals that were not included in reprogramming analysis.

Lastly, we may explore potential DNAme biomarkers that change in response to the intervention and are associated with clinically meaningful features (e.g. microbiome, lung function).

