#### 3.7 Hypothesis framework

For each of the primary, secondary, or subsidiary outcomes, the null hypothesis is that there is no true difference in effect between the baseline measurement and the measurement taken at 6 months.

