# 5 Statistical principles

# 5.1 Significance levels and adjustment of p-values for multiplicity

Significance levels throughout are set at p < 0.05. Formal adjustment for primary and secondary outcomes may be conducted using Benjamini-Hochberg or Bonferroni correction as appropriate, although formal adjustments may not be strictly necessary for outcomes of more exploratory or descriptive nature, as previously argued. For subsidiary outcomes, no formal correction will be applied. 95% confidence intervals will be presented for estimates of effects throughout.

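### Section 6.13.2 tests the reprogramming CpGs only for non-zero change from month 0 to month 6, so a general methylation drift could be read as an effect at those sites

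*SAP*

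**What the plan says.** Section 2.2.3 sets the objective: in a subgroup whose baseline cells are reprogrammed with Yamanaka factors (OSKM), find the altered sites, then see whether the intervention significantly alters the same or similar sites by month 6. Section 6.13 asks whether regions or CpGs that change on reprogramming "also change during the intervention, in both smoking cessation and intermittent fasting".

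For the analysis, Section 6.13.2 says that these regions "will be investigated in the same individuals at month 6, e.g. paired t-test mean or median methylation in significant CpGs", taken before and after reprogramming and before and after intervention. Regions that are consistent across participants may also be examined in women without reprogramming data.

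Section 3.7 covers every outcome, including subsidiary ones: "the null hypothesis is that there is no true difference in effect between the baseline measurement and the measurement taken at 6 months". Section 5.1 adds: "Significance levels throughout are set at p < 0.05" and "For subsidiary outcomes, no formal correction will be applied".

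The reprogramming row in Section 6.16 lists a paired before-after analysis in blood, with compliance, ketone bodies and factors found during exploration as covariates. Neither that row nor Section 6.13 names a background set, an enrichment test or a criterion for direction. Section 3.1 states that the study has no control group.

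**The concern.** These CpGs are of interest because reprogramming alters them. A significant month 0 to month 6 change in their mean or median will naturally be taken as something about those sites in particular, and Section 2.2.3 words it as an alteration caused by the intervention. The paired test shows only that the average at those CpGs moved. It does not show whether they moved more than other CpGs on the same arrays, or in the direction that reprogramming moves them.

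The distinction matters because nothing else in this design removes a common movement. Half a year of ageing, season, and any cell-mix or technical shift left after preprocessing could displace many CpGs together. The paired test would then correctly reject zero change, but the result would not be specific to reprogramming sites and need not be due to the intervention. What is at stake is the interpretation of one subsidiary result. The primary endpoint is unaffected.

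**Working it through.** **The plan's own figure.** The SAP gives no figure for this analysis. Its only sample-size statement (Section 3.6) concerns the WID index and reproduces as a paired design: 0.2 × √60 / 0.44 = 3.521, and Φ(3.521 − 1.960) = 0.941, against the stated 0.94. It does not bear on this point.

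**Inputs from the SAP.** Paired test on a mean or median per woman (6.13.2); null of zero change (3.7); significance level 0.05 (5.1), taken as two-sided because the SAP does not say.

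**Inputs assumed.**
- Between-woman SD of the array-wide shift: 0.5 percentage points of methylation.
- Reprogramming set: 500 CpGs, each with an SD of change of 3 points.
- Mean drift δ: 0, 0.1 or 0.25 points, with no effect specific to the set.
- Women n: 10, 20 or 60. The SAP does not state the subgroup size.

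**Paired test on the set alone.** The noise in a set mean is 3/√500 = 0.134 points. The SD of one woman's change is √(0.5² + 0.134²) = 0.518 points. The noncentrality is λ = δ√n / 0.518, and the rejection rate comes from the noncentral t with n − 1 degrees of freedom.

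| δ (points) | n | λ | critical t | rejection, formula | rejection, simulation (5,000 runs) |
|---|---|---|---|---|---|
| 0.1 | 10 | 0.61 | 2.262 | 8.5% | 8.7% |
| 0.1 | 20 | 0.86 | 2.093 | 13.0% | 12.2% |
| 0.1 | 60 | 1.50 | 2.001 | 31.3% | 31.7% |
| 0.25 | 10 | 1.53 | 2.262 | 27.7% | 28.3% |
| 0.25 | 20 | 2.16 | 2.093 | 53.6% | 53.3% |
| 0.25 | 60 | 3.74 | 2.001 | 95.7% | 95.2% |

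At δ = 0, λ = 0 and the rate is 5% at every n. Array offsets that vary between women but average to zero widen the denominator and do no harm. Only a systematic mean drift inflates the rate.

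**Same check in relative units.** A second simulation (20,000 runs) expressed drift in units of the between-woman SD of the shift, with residual SD 0.3 of that SD.

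| mean drift (SD units) | n = 10 | n = 30 | n = 60 |
|---|---|---|---|
| 0 | 5% | 5% | 5% |
| 0.25 | 10% | 25% | 45% |
| 0.5 | 28% | 73% | 95% |
| 1.0 | 77% | 99.9% | 100% |

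**Set minus background.** When both sets carry the same array shift, it cancels within each woman and the difference has mean zero. At δ = 0.25 the simulated rates are 4.6%, 5.6% and 5.1% for n = 10, 20 and 60. This follows from giving the background exactly the same shift. It shows what a well-matched background would achieve, not that any background will achieve it.

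**The case against.** Several points on the other side stand.

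- **The t-test is an example.** It follows an e.g., so a background comparison is not ruled out. It is still the only test offered, and Section 6.16 adds no other.
- **The test answers the literal question.** Sections 2.2.3 and 6.13 ask whether the sites also change, and a zero-change test matches the null in Section 3.7. Comparing with background is partly a change of estimand: if the intervention shifts methylation broadly, subtracting background removes a real effect. This is the strongest objection, and it is why the contrast belongs beside the planned test and not in its place.
- **Safeguards exist.** Section 6.4.1 keeps a woman's samples on one beadchip where possible, randomises timepoint position, normalises and allows batch correction. Section 6.13.1 applies that quality control here. Section 6 adjusts for cell composition, and Section 6.16 lists compliance as a covariate. Sections 5.3 and 6 allow a nested group of non-adherers if at least 10 exist per arm. These measures reduce drift or help to interpret it. None tests whether reprogramming sites differ from other sites, and the nested group is optional and not mentioned in 6.13.
- **The drift is assumed.** The SAP gives no value for drift, SDs, CpG count or subgroup size, and at the smaller drift with 10 women the inflation is slight.

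Two stronger readings should not be drawn. A reader might infer that the SAP claims lifestyle change imitates reprogramming; it makes no such claim. A reader might also take the within-individual wording of Section 2.2.3 to mean a separate verdict for each woman with CpGs as replicates. Section 6.13.2 tests a mean or median, which is one summary per woman and time point, so women are the replicates and the wording fits ordinary pairing.

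**Conclusion.** The concern holds in a limited form. As specified, the reprogramming analysis can show that the selected CpGs changed between month 0 and month 6. It cannot show that they changed more than other CpGs or in the reprogramming direction. A systematic drift left after preprocessing could therefore be read as an effect at reprogramming sites.

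Under the assumed values, a mean drift of 0.1 to 0.25 points gives significance in about 9-28% of studies with 10 women and 32-95% with 60. These figures are illustrations. They depend on a non-zero mean drift shared by the set, which the SAP neither states nor excludes. It would go too far to say that the test has an inflated error rate as such, or that any set of CpGs would pass: with no mean drift it holds 5%, and the SAP gives no ground for assuming that drift is uniform across the array.

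Severity is low, because the analysis is subsidiary and the study is described as predominantly exploratory.

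**What to change.** In Section 6.13.2:

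1. Keep the paired month 0 to month 6 test.
2. Add, for each woman, the change in her reprogramming CpGs minus the change in background CpGs from the same arrays, matched on baseline methylation, probe type and immune-cell dependence. Test this difference across women and state that the woman is the unit of analysis.
3. Report whether the change goes in the OSKM direction. If one month 0 array is the starting point for both changes, its measurement error pushes both the same way, so treat agreement in direction as supporting evidence only.
4. Report overlap of site lists as enrichment over the matched background.
5. State that any claim of a reprogramming-specific effect rests on the contrast in item 2, and that the paired test alone supports only a statement of change.

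The cost is SAP wording and some programming to build the background set, with no new samples or arrays. The drawback is that the contrast may remove a genuine array-wide effect of the intervention, so both results should be reported.

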# 6.14 Subsidiary analysis: meaningful biomarkers of intervention

Many studies have previously identified signatures that that capture epigenetic ageing yet the biological meaning of them remains unclear. It may be beneficial to identify CpG markers that are changed in response to a putative health-promoting intervention specifically and correlate with clinically meaningful changes (e.g. gut microbiome, lung function) in a well-characterised longitudinal dataset. We may chose to undertake this subsidiary analysis pending the outcome of initial results. This analysis is largely explorative and may depend on the data. DNA methylation features associated with the intervention and changes in other biologically meaningful changes (e.g. microbiome, lung function) may be identified. Scores can be investigated in a hold-out test set and ongoing follow-on projects at our institute (SUN and LIFE Tirol), which investigate smoking cessation in n=200 participants and randomised intermittent fasting in approximately n=800 participants.

# 6.15 Additional exploratory analyses

Post-hoc analyses requested by journal editors or referees, as well as exploratory analyses, will be labelled explicitly as such. Any further analyses not specified in the analysis protocol will be exploratory in nature and may be documented in a separate statistical analysis plan(s).

# 6.16 Tabular summary of analyses

· —										
Notes	Comparison between ran- domised arms and subgrouns for	different fasting patterns Comparison between ran- between arms and subgroups for different fasting	patterns		Association with epigenetic and genetic factors Association with epigenetic and genetic factors	Association with epigenetic and genetic factors	Association with epigenetic and genetic factors	Association with epigenetic factors	Associateion with epigenetic factors	
Tissue	cervix	cervix	cervix cervix, buccal, blood - separate and combined	cervix, buccal, blood - separate and combined	n/a n/a	n/a	n/a	blood	blood	fecal
Adjustments, co- variates	ic	j	ic, age, e.g. BMI, compliance score ic, BMI, age, other markers associated	ic, BMI, age, other markers associated	compliance, co- variates identified during exploration compliance, co- variates identified during exploration	compliance, co- variates identified during exploration	compliance, co- variates identified during exploration	compliance, co- variates identified	during exploration compliance, co- variates identified during exploration	
Study populations	All included ITT	Per protocol (280% com- biance) or above/below me- dian compliance	score TTI TTI	Per protocol (280% com- pliance) or above/below me- dian compliance	score ITT Per protocol (≥80% com- pliance) or above/below me-	dian compliance score ITT	Per protocol (280% com- pliance) or above/below me- dian compliance	score	Per protocol (≥80% com- pliance) or	dian compliance score Lean versus obese, smokers versus
Type of analysis	Descriptive statis- tics Paired before- after	Paired before- after	Longitudinal (linear/non-linear mixed-effects models) Longitudinal (linear/non-linear mixed-effects	models) Longitudinal (linear/non-linear mixed-effects models)	Paired before- after Paired before- after	Longitudinal (linear/non-linear mixed-effects	models) Longitudinal (linear non-linear mixed-effects models)	Paired before- after	Paired before- after	Baseline compari- son
Value	Epidemiological data Epigenetic WID scores	Epigenetic WID scores	Epigenetic WID scores Epigenetic WID markers	Epigenetic WID markers	Clinical and epidemiological markers and Clinical and epidemiological markers	Clinical and epidemiological markers	Clinical and epidemiological markers	Mutation data	Mutation data	Microbiome data
Outcome	Baseline Primary		Secondary							

		Association with epigenetic and clinical factors	Association with epigenetic and clinical factors	Association with epigenetic and clinical factors	Association with epigenetic and clinical factors	Association with ketone levels,	Association with epigenetic factors	Association with epigenetic factors				Association with epigenetic factors	Association with epigenetic factors	
fecal	fecal	blood	blood	blood	blood	urine, saliva	skin biopsy	skin biopsy	n/a	n/a		blood	blood	all
compliance, weight loss, co- variates identified during exploration	compliance, weight loss, co- variates identified during exploration	compliance, weight loss, co- variates identified during exploration	compliance, weight loss, co- variates identified during exploration	compliance, weight loss, co- variates identified during exploration	compliance, weight loss, co- variates identified during exploration		compliance, weight loss, co- variates identified during exploration	compliance, weight loss, co- variates identified during exploration				compliance, ke- tone bodies, factors identified	during exploration compliance, ke- tone bodies, factors identified	during exploration
TTI	Per protocol (280% com- pliance) or above/below me- data compliance	TTI	Per protocol (280% com- pliance) or above/below me- datan compliance	LLI	Per protocol (280% com- pliance) or above/below me- dian compliance		ITT	Per protocol (280% com- pliance) or above/below me- datan compliance	LLI	Per protocol (280% com- pliance) or above/below me- data compliance		ITT (subgroup of all participants in- cluded for single-	cell sequencing) ITT	all
aired before- ter	aired before- ter	aired before- ter	aired before- ter	ongitudinal inear/non-linear ixed-effects odels)	ongitudinal inear/non-linear ixed-effects odels)	cploratory, efore-after	aired before- ter	aired before- ter	aired before- ter	aired before- ter	escriptive statis- cs	aired before- ter	aired before- ter	xploratory, lon- tudinal
Microbiome data P i af	Microbiome data P: af	Blood data Pa	Blood data P: af	Blood data Lc (1i m m	Blood data LG (I) m m	Metabolomic data ex	Skin data Pa	Skin data P: af	Psychological data Pa	Psychological data Pa	Continuous com- D	Single-cell se- Pe quencing af	Reprogramming af	Biomarkers of in- tervention gi
											Subsidiary			

